1.4.9 Data Analysis

The researcher assistant who performed the randomization will register all neonatal data, discharge variables and the follow-up data, during the appointments. Motor performance of the infant will be assessed using TIMP at 40 weeks, 1 month, 2 months and 3 months of corrected age and neurodevelopment will be assessed using RNDA. Scores of TIMP items and items from RNDA will be transformed from categorical scale to a continuous scale. The Rasch Unidimensional Measurement Model (RUMM) will be used for this process. The number of sessions and amount of time spent performing the intervention will be recorded and analyzed. All the variables will have double data entry.

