1.4 Study design

The proposed study will be single-center, prospective, double-blinded randomized controlled trial (RCT) to study the effect of physical therapy intervention on motor performance of infant born preterm.

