1.4.7 Data Collection

The study will be conducted after seeking ethical approval from Institutional Review Board (IRB), Khesar Gyalpo University of Medical Sciences of Bhutan (KGUMBS). The data will be collected at pediatric physiotherapy unit, JDWNRH. Preterm infants referred for high risk follow up clinic at Pediatric Physiotherapy Unit that evaluates neurodevelopmental outcome will be recruited. Oral and written information will be given to parents of the preterm babies fulfilling the inclusion criteria. Parents will be informed regarding the objectives, procedures, risk and benefits of the study. Informed consent will be taken from the parents prior to the study by the principal investigator. Strategies to achieve adequate participant enrolment to reach target sample size will be, establish a link between

the research team and mother and father of each of the subjects included, regardless of the group allocated since randomization.

Randomization will be performed by blindly drawing the slip from the container which will have equal numbers of same size and shape slips and will be performed by the research assistant who will not be responsible for any intervention nor outcome assessment. After randomization the infants in the control group will receive standard care and the infants in the intervention group will receive modified SPEEDI. The principal researcher will provide the modified SPEEDI. The research assistants shall be physical therapist or physical therapy assistants and occupational therapist who has over 2 years of experience in working with pediatric population and will be blinded to the group allocation since they will assess the outcome. These research assistants will be trained to use the measurement tools by the principal researcher. As the study participants are preterm infants, caution will be taken to avoid thermal stress to these infants by keeping the data collection room in pediatric physiotherapy unit warm. During the study process if there are amendments to the study protocol, the information shall be communicated with the IRB and the co-investigators of the study.

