1.4.8 Measurement

Prior to the assessment of motor performance and neurodevelopment, demographic details such as gestational age, length of stay in the hospital and medical diagnosis will be recorded. The measurement will be taken at 40 weeks of post menstrual age, 1 month, 2 months and 3 months of corrected age by the research assistants who will be blinded to group assignment.

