Standard care group will include education regarding early development which is present in the mother and child handbook and which is currently practiced. The standard care group will also be required to visit the clinic monthly and assessment will be performed monthly until the infant is 3 months of corrected age. During the monthly visit parents will be asked to report the amount of time spend with their infant performing the activity.

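### The assistant who draws the allocation slips is also assigned to register follow-up data at the visits, which weakens the protection that blinded assessors provide

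*Combined protocol and SAP*

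**What the plan says.** Section 1.4.7 describes the allocation: "Randomization will be performed by blindly drawing the slip from the container". It adds that the draw "will be performed by the research assistant who will not be responsible for any intervention nor outcome assessment". The same section says that the research assistants who measure outcomes "will be blinded to the group allocation since they will assess the outcome", and section 1.4.8 repeats that measurements are taken "by the research assistants who will be blinded to group assignment". Section 1.4 calls the trial double-blinded.

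Section 1.4.9 then assigns the data work: "The researcher assistant who performed the randomization will register all neonatal data, discharge variables and the follow-up data, during the appointments". Its next sentence turns to the TIMP at the four time points and to the RNDA. The only safeguard it gives is "All the variables will have double data entry", without saying who makes the entries or whether they know the arm.

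Compliance information also arises at the visits. For the standard care group, section 1.4.8.4 says: "During the monthly visit parents will be asked to report the amount of time spend with their infant performing the activity". The plan does not say who asks.

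**The concern.** Section 1.4.7 sets up a separation: the person who performs the draw has no hand in outcomes. Section 1.4.9 identifies its data registrar as the person who did the randomisation, so this is not a second assistant who happens to share the title. It places that person at the appointments with the follow-up data. This is a stated assignment that works against the separation, rather than a detail left out.

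It matters because little else protects the outcomes. The principal researcher delivers the intervention and the parents carry it out, so neither can be blind. Protection against detection bias rests on assessors who do not know the arm, and both instruments depend on observing and handling the infant. A colleague at the visit who knows the arm can give it away without meaning to. If that colleague also handles the scores or asks parents about time spent, knowledge of the arm can affect what enters the dataset. With 14 infants planned per group, a few affected records could carry weight.

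**Working it through.** The point is mainly about roles, so the sections are set side by side first and the records counted afterwards.

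**Roles**

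| Task | Who | Knows the arm? | Section |
|---|---|---|---|
| Draws the slip | A research assistant with no intervention or assessment role | Yes, by inference: no text hides the result from the drawer | 1.4.7 |
| Delivers modified SPEEDI | Principal researcher | Yes | 1.4.7, 1.4.8.4 |
| Administers and scores the TIMP | Other research assistants | No | 1.4.7, 1.4.8, 1.4.8.1 |
| Administers the RNDA, with responses recorded during administration | Other research assistants | No | 1.4.7, 1.4.8, 1.4.8.2 |
| Registers follow-up data at appointments | The assistant who drew the slips | Yes, by the same inference | 1.4.9 |
| Asks parents about time spent | Not stated | Not stated | 1.4.8.4 |
| Makes the two data entries | Not stated | Not stated | 1.4.9 |

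The first and fifth rows are the same person. Scoring stays with blinded staff. The conflict lies in who is present at the visit and who handles the data.

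**What counts as follow-up data.** The term is not defined. The TIMP and RNDA are named immediately afterwards and nothing restricts the term to administrative items, so including both instruments is the natural reading, though not an explicit one.

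**What double entry can do.** It detects disagreement between two keyings of a source. It cannot detect a source that was itself affected by knowledge of the arm. Which case applies depends on who completes the source form, and section 1.4.9 does not say.

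**Records affected**

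Inputs: 28 infants, 14 per group (section 1.4.5); assessments at 40 weeks' postmenstrual age and at corrected ages of 1, 2 and 3 months (section 1.4.8).

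The plan's total reproduces. With d = 1.29, and assuming a two-sided alpha of 0.05 and 80% power (the readable text gives neither the sidedness nor the power), a two-sample t-test needs 11 per group, 22 in all, with power 0.82. Allowing for 20% dropout, 22 / (1 − 0.20) = 27.5, rounded up to 28.

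Records per instrument = infants × visits after the draw:

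- Slip drawn after the 40-week assessment: 28 × 3 = 84.
- Slip drawn before it: 28 × 4 = 112.

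The readable text does not place the draw before or after the 40-week assessment, and the procedure figure (Figure 3) is not available, so both counts are given. Both are maxima before dropout. If only the 22 infants of the original calculation gave post-baseline data, the first count would be 22 × 3 = 66.

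These are counts of records, not estimates of bias. The documents give nothing from which a shift in scores could be calculated.

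**The case against.** The strongest reply is that registering means no more than logging completed scores. There is good support for it. Section 1.4.8 gives measurement to blinded staff. Section 1.4.8.1 treats scoring the TIMP as part of the tester's session and provides for unfinished items in a second session within 24 hours. Section 1.4.8.2 has RNDA responses recorded as the test is given. Section 1.4.11 mentions filled proformas kept under lock, so paper source forms exist, and double entry would make transcription checkable against them.

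Much of this stands, and it rules out several stronger readings. A reader might infer that outcome recording as a whole is unblinded, or that the registering assistant settles borderline or incomplete items. The documents do not support either: they place scoring with the blinded tester and give the registrar no discretion over items. A reader might also infer that this assistant keeps a full allocation list. No list is described, and the text supports only that the drawer learns each arm at the draw. Nor can it be said that all 112 records per instrument are exposed, since baseline may precede the draw.

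The reply does not remove the assignment itself. No section says who fills in the proforma, or that the assessor's scores are fixed before the randomising assistant handles them. Even if registering is pure transcription, section 1.4.9 still has someone who knows the arm at the appointments, where disclosure to the assessor is possible. If that person also asks for parent-reported time, there is no blinded score behind that figure to check it against.

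**Conclusion.** The point holds in a limited form. Sections 1.4.7 and 1.4.9 give the randomising assistant roles that do not fit together, and the result weakens the assessor blinding on which the trial depends. The exposure is presence at visits, handling or transcription of scores, possible collection of parent-reported time, and possible disclosure of the arm. Unblinded scoring of the TIMP or RNDA is not shown.

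Up to 84 post-baseline records per instrument are touched, or 112 if allocation precedes the 40-week assessment, before dropout. The direction and size of any bias cannot be derived.

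This rests on two inferences: that the person drawing the slip sees the result, and that follow-up data includes the TIMP and RNDA scores. If the second were wrong, the concerns about disclosure at the visits and about parent-reported time would remain. The inconsistency should be corrected. It does not by itself invalidate the design.

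**What to change.** Revise section 1.4.9, and align section 1.4.7 with it, so that:

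- The blinded assessor completes the TIMP and RNDA score forms under a study ID and signs them when the assessment is complete. Where section 1.4.8.1's second session is used, signing follows that session.
- Both data entries are made from the signed forms by existing staff who do not know the allocation. This excludes the principal researcher, who delivers the intervention.
- Parent-reported time is collected by someone other than the randomising assistant where possible. If that person is an outcome assessor, it should follow the scoring, because what parents say may reveal the arm.
- The randomising assistant registers only neonatal and discharge variables and does not attend outcome assessments.

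The change needs no additional infants or visits. It moves tasks among staff and adds a little paperwork for the assessors. The plan does not state how many research assistants there are, so the sponsor should confirm that staff unaware of allocation are available for data entry.

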1.4.5 Sample size

Sample size calculation will be based on the study by Dusing et al(43). According to the study they found a significant difference in motor performance of infants born preterm who received physical therapist delivered intervention compared to the usual care group. The effect size from the study was Cohen's d of 1.29 for TIMP z- score. Using this data, the total sample size of 22 was obtained using G power program version 3.1. However, with 20% drop out rate a total of 28 infants born preterm would be required with 14 in each group.

[figure not shown]

Figure 2: G power

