1.4.6 Variables

Independent variable

1. Groups: Intervention group and standard care group
2. Time: At baseline, 1, 2 and 3 months of corrected age

Dependent variable

1. Motor performance
2. Neurodevelopment
3. Compliance

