1.4.8.1 Motor performance

Motor performance will be assessed using The Test of Infant Motor Performance (TIMP) version 5.1, administered when the child is awake (Brazelton state 3,4 or 5). The infant should wear minimal clothing as possible. Testing will be performed on a firm surface with no distractions. No more than 3 trials will be allowed for each elicited item. If the infant gets fussy and irritable during the process of assessment, breaks can be taken in between the assessment and if the parents are not comfortable with the procedure the parents will have every right to withdraw and discontinue their infant's participation from the study. However, if the parent consents to continue the assessment, items that remain during the first session shall be

completed in second session within 24 hours so that it assessor does not have to redo the whole assessment again.

The Test of Infant Motor Performance (TIMP) was developed to assess functional motor performance in infants from 34 weeks postmenstrual age (PMA) through 4 months corrected age. The TIMP is a 42- item assessment with 13 dichotomous items scored based on observation of spontaneous movement and 29 elicited items with 4 to 7-point rating scales based on handling of the infant in a variety of positions in space. The test takes 20-35 min to administer and score with variation based on age and tolerance of the infant and the experience of the tester. It has been described as one of the best tools to discriminate between age-appropriate and delayed motor performance in preterm and term infants, and to predict later motor development. The TIMP is a valid and reliable tool developed to detect typical and atypical performance in preterm infants and evaluate the effect of an intervention on the infant motor performance(44-46). The assessment tool has been also used in multiple clinical trials to evaluate the effectiveness of therapy intervention.

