1.4.8.2. Neurodevelopment

Neurodevelopment will be assessed using the Rapid Neurodevelopmental Assessment (RNDA), administered when the child is awake and there should be no distraction and prompting allowed from parents while performing the assessment. While administering the assessment the response elicited from the infant will be recorded.

The Rapid Neurodevelopmental Assessment (RNDA) tool is a reliable and valid developmental assessment tool for use by multidisciplinary professionals in developing country to assess the neurodevelopmental status of children from 0-24 months(47). The tool has been a useful to identify neurodevelopmental impairment (NDI) in resource limited settings where there is lack of trained professionals to identify children with neurodevelopmental impairments. It assesses developmental domains such as primitive reflexes (0 to <1 month), gross motor, fine motor, vision, hearing, speech, cognition, behavior and seizures. It helps to identify impairments in these developmental domains and categorizes into three degrees of impairments which are mild, moderate and severe impairment.

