1.4.10 Statistical Analysis

Statistical analysis will be performed using Statistical Package for Social Sciences (IBM SPSS statistics for windows, version 28). Shapiro Wilk test will be used to test for normality of data. Descriptive statistics will be used to analyze patient's demographic data. To investigate the effect of physical therapist intervention on motor performance two-way mixed ANOVA will be performed. To investigate the effect of physical therapy intervention on neurodevelopment two-way mixed ANOVA will be performed. The level of significance will be set at a p-value < 0.05.

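### Does it matter that the plan does not name the TIMP score for the ANOVA, or say how the Rasch measure is calibrated and linked across the four visits?

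*Combined protocol and SAP*

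**What the plan says.** The relevant text is spread over several sections of the combined protocol and SAP.

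- **1.4.5 Sample size** takes from the source study a Cohen's "d of 1.29 for TIMP z- score" and derives 22 infants, raised to 28 for 20% dropout. The z-score is mentioned nowhere else.
- **1.4.6 Variables** lists the outcome only as "1. Motor performance".
- **1.4.8 Measurement** sets four assessments: "The measurement will be taken at 40 weeks of post menstrual age, 1 month, 2 months and 3 months of corrected age".
- **1.4.8.1** describes the TIMP as 13 dichotomous items plus "29 elicited items with 4 to 7-point rating scales", and names no summary score.
- **1.4.8.2** lists the RNDA domains as "primitive reflexes (0 to <1 month), gross motor, fine motor, vision, hearing, speech, cognition, behavior and seizures".
- **1.4.9 Data Analysis**: "Scores of TIMP items and items from RNDA will be transformed from categorical scale to a continuous scale". The next sentence gives the method: "The Rasch Unidimensional Measurement Model (RUMM) will be used for this process".
- **1.4.10 Statistical Analysis**: "To investigate the effect of physical therapist intervention on motor performance two-way mixed ANOVA will be performed". An equivalent sentence covers neurodevelopment.

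**The concern.** An analyst working from this text finds one score in the sample size section, another in the data analysis section and none in the ANOVA sentence. Three choices are unwritten: which TIMP score is analysed, whether item parameters are external or estimated from this trial, and how the visits are put on one scale. For RNDA there is also the question of scaling by domain or overall, and of reflex items that stop applying after the first month.

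The stake would be the four-visit comparison in section 1.3.1. An age-standardised z-score removes expected growth and a Rasch measure keeps it, so the two can disagree on the group-by-time term. If the score were picked after the data were seen, a reader could not tell whether the verdict depended on that choice. Calibration within the trial also looks thin, and separate calibration at each visit would leave growth on an unlinked scale.

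**Working it through.** **1. The plan's own figure.** Inputs from 1.4.5 and 1.4.10: d = 1.29, equal arms, alpha 0.05, 20% dropout. Assumed, because the text does not give them: two-sided t-test, 80% power. The noncentral t gives 11 per group, 22 in total (power 82.1%), and 22 / 0.8 = 27.5, rounded up to 28. Both stated numbers reproduce, so the only question is whether d = 1.29 carries over to another scale.

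**2. Which score enters the ANOVA.** Section 1.4.9 builds one continuous TIMP measure and 1.4.10 analyses motor performance directly afterwards. No analysis section mentions a z-score. In 1.4.5 it is the unit in which another study reported its effect, which makes it a planning assumption and not a second candidate outcome.

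**3. Amount of data for calibration.** TIMP thresholds number 13×1 + 29×3 = 100 to 13×1 + 29×6 = 187. Set against 28×4 = 112 infant-visits this looks hopeless, but thresholds are estimated from item responses: 42×112 = 4,704 if complete, or 4,704/187 ≈ 25 to 4,704/100 ≈ 47 per threshold. These are clustered within infants, but far more than 112.

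**4. What unlinked visits do to a group comparison.** Suppose calibrating visit *t* alone turns a measure *m* into a_t + b_t·m. Both arms share a_t and b_t. The group difference at that visit becomes b_t × (difference): the shift a_t cancels, and only unequal units b_t can disturb the group-by-time term.

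**5. Simulation.** Assumptions: partial-credit data on 13 dichotomous and 29 polytomous items, two equal arms, z-scores from simulated age norms. In the base case ability SD is 0.6, between-visit correlation 0.6, growth 1.0 logit per month, and the effect rises from 0 at baseline to d = 1.29 at 3 months. There were 400 runs per main scenario (standard error about 2 points), with calibration on the trial's own data.

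| Comparison | Result |
|---|---|
| Each visit alone v joint calibration, group-by-time verdict | differs in 2% to 5% |
| Each visit alone v joint calibration, growth | 67% to 79% of the joint value (base case 2.5 v 3.6 logits) |
| z-score v Rasch, 3-month effect | mean d 1.18 v 1.19 |
| z-score v Rasch, 3-month verdict | differs in 3% to 6% (28 infants), 7.5% (22) |
| z-score v Rasch, group-by-time verdict, true effect | differs in 12% to 16% (28 infants, main scenarios), 19% to 28% (two other ability assumptions), 22% (22 infants) |
| z-score v Rasch, group-by-time verdict, no effect | differs in 2%; false positives not raised |

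**6. Reading the 16.3% base-case disagreement.** Group-by-time power was 0.80 (Rasch) and 0.68 (z-score). Let *a* be the share significant on Rasch only and *b* on z only. Then a − b = 0.12 and a + b = 0.163, so a ≈ 0.14 and b ≈ 0.02. The disagreement is mostly the Rasch measure detecting a true effect that the z-score misses, in data generated from a Rasch-type model, which favours it.

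**7. Calibration source.** A separately coded simulation with item parameters fixed at their true values (the external-calibration case) gave base-case Rasch power of 0.82, against 0.80 with in-trial calibration. The two programs also differ in threshold spread, so this is only a rough check, but it shows no material loss from calibrating within the trial.

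**The case for a change.** The strongest case for a change is that implication settles only the first of the three choices. Whoever runs the analysis must still decide on external or in-trial parameters and on joint or separate calibration. The separately coded simulation also found z-score and Rasch group-by-time verdicts differing in 11% to 21% of trials with a true effect, so that disagreement does not come from one program or one calibration method. Writing the choices down before the data are seen would cost a few sentences.

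What stands is the silence on calibration and linking. It does not reach the conclusions:

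- The 11% to 21%, like the 12% to 28% at 28 infants, compares Rasch with a score the analysis sections never propose. Moving to it later would be a visible departure from 1.4.9.
- The choice that is open, joint or separate calibration, moves 2% to 5% of group-by-time verdicts. Growth does shrink under separate calibration, but sections 1.3 and 1.3.1 ask for differences between groups.
- A smaller standardised effect on the Rasch scale would cost power: with 22 infants, 61% at d = 1.0 and 43% at d = 0.8. Those effects are assumed values. Nothing in the documents points to them, and the simulated 3-month effects were nearly equal.
- The RNDA point cannot be sized, because the documents do not list items by age. It also depends on reading the reflex age limit as corrected age.

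**Conclusion.** No change is needed. The plan leaves out detail that an analyst would fill in the ordinary way: analyse the Rasch measure that 1.4.9 creates, with item parameters either taken from outside or estimated once from all visits pooled. Group does not enter such a calibration, so it gives no route to favouring an arm. Nothing in the documents shows a biased or weaker group comparison, and the borrowed d = 1.29 is an ordinary planning assumption.

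The sizes behind this are 2% to 5% of group-by-time verdicts changed by the least favourable calibration choice examined, a 3-month effect of 1.18 against 1.19 on the two scales, and no rise in false positives. They rest on simulated ability, growth and age norms that the documents do not supply, and on a generating model that favours Rasch. The conclusion on which score is analysed rests on the text alone.
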